1. STUDY OBJECTIVES

1.1 Primary Objective

Examine the effectiveness at 3 months of two care pathways for LBP: 1) an integrated care pathway (ICP) and 2) a coordinated care pathway (CCP). We will test the central hypothesis that the ICP will reduce pain interference with normal activities and improve physical function, as measured by PROMIS Short Form scores when compared to the CCP.

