3. STUDY DESIGN

An overview of this 4 year cluster randomized embedded pragmatic trial is presented in **Figure 3** and SPIRIT Table³⁷ is included in the **Appendix IV**. We will compare the effectiveness of two care pathways for LBP. The trial will test the central hypothesis that patients in the ICP will have reduced pain interference and improved physical function compared to patients in the CCP. We are testing these two care pathways in a comparative effectiveness approach because both have the potential to deliver guideline adherent, biopsychosocial-oriented care but they have different implementation approaches.

VA primary care clinics that have agreed to have their clinical staff trained in offering these care pathways as standard care will be randomly assigned to one of the two care pathways. A cluster randomized trial (CRT) was selected because it offers the most pragmatic and efficient design to address our aims due to the nature of the care pathways and interest in assessing both short and long-term outcomes. An important consideration in a CRT is the optimal unit of randomization. We will designate the unit of randomization as the VA clinic (rather than an entire VAMC 'site' or 'station') to 1) enhance feasibility of implementation, and 2) improve power (higher number of clusters).

Figure 3. Study Design Overview

Veteran outcomes will be collected in the EHR at baseline and at 3-months follow up and for a subset of Veterans, surveys will be administered at baseline with follow up points at 3, 6, 9, and 12 months (see Section 10 - Measures and Data Collection). The primary outcomes (PROMIS short forms for pain interference and physical function, 4 items each) and secondary outcome (PROMIS short form sleep quality) will be captured in the VA medical record by clinical providers using templates provided by the research team (see Section 6 - Study Procedures). Veteran participants (n=848) will be consented for the additional survey data collection by Durham VA study staff (baseline) and DCRI's Outcomes Call Center (3, 6, 9, and 12 month follow-up calls).

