9.3 Definition of Populations

As this is an embedded pragmatic trial, all adult subjects that present to clinics with LBP and are referred to one of the two arms of the trial with initial contact with pain navigator or central delivery for data collection will be eligible for the primary analysis as part of the administrative sample. A subset of these Veterans will be enrolled as research subjects so that more detailed research data can be collected at regular intervals for follow up. For this subgroup, equivalent numbers of Veterans with LBP will be enrolled at each clinic.

The primary analyses will be conducted on an intention-to-treat basis; patients will be analyzed in the group to which they were randomized, regardless of intervention adherence, using all available data. The main conclusions drawn from this trial will be based on the pre-specified hypotheses outlined below and will be tested with two-sided p-values at the standard 0.05 level, except where noted due to multiple primary outcomes. For all study outcomes, we will interpret differences between groups over time with reference to prior literature regarding clinically meaningful changes. Results from exploratory analyses will be interpreted with appropriate consideration for their exploratory nature. Statistical analyses will be performed using the latest release of SAS for Windows (Cary, NC) and R software.

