9.6 Data Analyses

Aim 1 Analyses

The primary outcomes are continuous and will be ascertained at the planned baseline and follow-up assessment (3 months) from administrative data collected from the EHR on all eligible LBP Veterans presenting at participating clinics. Changes in pain interference and/or physical function scores will be estimated and the primary hypotheses tested via hierarchical linear mixed-effects models with patients nested within clinics and baseline and 3 month values in the response vector.⁵⁵ Hierarchical linear models are a flexible and powerful analytic tool for clustered longitudinal continuous outcomes. The fixed-effect portion of the model will have the form: $Y_{ijk} = \beta_0 + \beta_1 * (followup) + \beta_2 * (followup * intervention)$ for clinic i , patient j , at time k . Random effects (clinics and time by clinics) will be included in the model to account for clustering of patients within clinics as the clinics are the unit of randomization, random effects will also be included to account for the within-patient correlation between repeated measures over time. We will assess the best fitting random effects structure by fitting a variety of random coefficient models (e.g., random intercept only, random intercept and linear slope) and assess using Akaike Information Criteria (AIC) model selection criteria.^{56,57} The predictors in the model will include a time effect and indicator variables for treatment interacting with the time effect. The intraclass correlation capturing the relationship of outcomes between patients seen at the same clinic is accounted for via the random effects for the clinics and time by clinics, which are assumed to be normally distributed. The model will be fit in the SAS procedure PROC MIXED using full likelihood approximation and the hypotheses will be tested by whether the estimated coefficient β_2 is positive and significantly different than 0 at the 0.025 level due to 2 primary outcome variables. We will include covariates used in the covariate constrained randomization⁴ (5 potential variables; average pain scores, clinic location (main medical center/community clinic), number of participating primary care providers, average level of opioid exposure of LBP patients at clinic, and average age of LBP patients at clinic) in our primary model as well as a limited number of patient-level covariates that are readily available in the EHR (age, gender, race and a comorbidity measure). While we have procedures in place to monitor timing of the 3-month follow-up assessment in the EHR, if we have a significant number of assessments outside the 1-month window for the 3-month assessment that are dropped from the primary analysis, we will conduct a sensitivity analysis including the assessments outside the window and estimating a 3-month treatment effect from this model.

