$\beta_1^*(\text{moderator}) + \beta_2^*(\text{moderator}^*\text{intervention}) + \beta_3^*(\text{followup}) + \beta_4^*(\text{followup}^*\text{intervention}) + \beta_5^*(\text{moderator}^*\text{followup}) + \beta_6^*(\text{moderator}^*\text{intervention}^*\text{followup})$ for clinic i , patient j , at time k . A random effects (clinics and time by clinics) will be included in the model to account for clustering of patients within clinics, as the clinics are the unit of randomization. Differential change in pain interference or function by moderator for the two intervention groups is supported if the coefficient for β_6 is significantly different than zero at the $p=0.025$ level. For the adherence multinomial outcome, we will fit a generalized linear model with a random effect for clinic and cumulative logit link function. As the adherence outcome is potentially a 3-level outcome there will be two interaction terms to examine for moderation effects (e.g. whether the effect of the intervention by chronicity is different for those moderately adherent vs. not adherent and/or those fully adherent vs. not adherent).

Exploratory analyses to identify multidimensional subgroups from combinations of baseline characteristics (e.g. age, sex, opioid use) for treatment moderation of the primary outcomes of pain and function as well as per protocol adherence to treatment.

Patients are likely to vary in treatment response. This variation is known as heterogeneity of treatment effects (HTE). Exploration of HTE has typically focused on one-factor-at-a-time post-hoc subgroup analyses (as described in our planned subgroup analysis); however, it is possible to instead identify multidimensional subgroups exhibiting HTE. In particular, we will apply the data-driven method GUIDE⁶⁶(Generalized, Unbiased, Interaction Detection and Estimation) that can be used for longitudinal outcomes, so can incorporate all follow-up outcomes at 3 and 12-months, as well as multi-response outcomes. GUIDE uses a regression tree algorithm that identifies subgroups with heterogeneous effects and estimates how the treatment effect varies across the subgroups. We will include baseline demographic (e.g. age, sex, race) and clinical characteristics (e.g. LBP chronicity, opioid use, comorbid conditions) that are available from EHR. GUIDE provides bootstrap confidence intervals for the treatment effects of identified nodes and is available via a software package.

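### The Aim 1 success rule requires a positive coefficient for both primary outcomes, although they are hypothesised to move in opposite directions, so its sign is wrong for one of them

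*Combined protocol and SAP*

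**What the plan says.** The primary objective (Section 1.1) is to test whether the "ICP will reduce pain interference with normal activities and improve physical function, as measured by PROMIS Short Form scores when compared to the CCP". Section 3 repeats the directions: "patients in the ICP will have reduced pain interference and improved physical function compared to patients in the CCP".

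Section 9.6 (Aim 1 Analyses) gives one mixed model for both outcomes. Its fixed part is an intercept, a follow-up term (β₁) and a follow-up-by-intervention term (β₂), with "baseline and 3 month values in the response vector". The arms enter through "indicator variables for treatment interacting with the time effect", and the text does not say which arm is coded 1. The hypotheses are then tested by whether β₂ "is positive and significantly different than 0 at the 0.025 level due to 2 primary outcome variables".

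Two other passages bear on this rule. Section 9.3 says that the pre-specified hypotheses "will be tested with two-sided p-values at the standard 0.05 level, except where noted due to multiple primary outcomes". The Aim 2 rule in Section 9.6, for the same two outcomes, asks only that the three-way interaction β₆ be "significantly different than zero at the $p=0.025$ level" and sets no sign.

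**The concern.** One sign cannot be right for two separately tested outcomes whose hypothesised effects point in opposite directions. This sentence is the pre-specified decision rule for the trial's central hypothesis. Taken as written, it cannot declare an ICP benefit on one of the two primary outcomes, and it would count a significant worsening on that outcome as support.

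Direction matters in this trial. CCP is an active comparator that the précis describes as less resource intensive, so a result favouring CCP would be informative and needs a stated reading. Section 6.3 also says that the study statisticians are not blinded to clinic assignment, which is a reason to fix coding and direction in writing before the outcome data are analysed.

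**Working it through.** **Step 1: what β₂ measures.** The model has no intervention main effect, so the arms share a baseline mean. At 3 months the mean is β₀ + β₁ in the arm coded 0 and β₀ + β₁ + β₂ in the arm coded 1. β₂ is therefore the between-arm difference in change, in the units and orientation of the score.

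**Step 2: sign expected under the hypothesis.** This takes higher pain interference as worse and higher physical function as better.

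| Arm coded 1 | Pain interference | Physical function | Outcome for which 'positive' is wrong |
|---|---|---|---|
| ICP | β₂ < 0 | β₂ > 0 | Pain interference |
| CCP | β₂ > 0 | β₂ < 0 | Physical function |

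Exactly one outcome fails under either coding. The protocol text does not reverse either scale, define the response as improvement, or set a sign per outcome.

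**Step 3: reproduce the plan's detectable effects.** Inputs from Section 9.2 and Table 8:
- g = 8 clinics per arm and m = 84 patients per clinic at follow-up
- over-time correlation 0.50
- alpha 0.025 and power 90%
- ICC 0.01, 0.02 and 0.05

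The sentence giving the correlation is incomplete after its mention of patients. Applying 0.50 at clinic level as well is an assumption.

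SE = √{4[(1 − ICC)(0.5) + m·ICC·(0.5)] / (m·g)}

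- ICC 0.01: √{4(0.495 + 0.420)/672} = 0.0738
- ICC 0.02: √{4(0.490 + 0.840)/672} = 0.0890
- ICC 0.05: √{4(0.475 + 2.100)/672} = 0.1238

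Detectable effect = (t₀.₉₈₇₅ + t₀.₉₀) × SE.

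| Degrees of freedom | Multiplier | ICC 0.01 | ICC 0.02 | ICC 0.05 |
|---|---|---|---|---|
| 9 (16 − 2 − 5) | 2.685 + 1.383 = 4.068 | 0.300 | 0.362 | 0.504 |
| 10 (16 − 2 − 4) | 2.634 + 1.372 = 4.006 | 0.296 | 0.356 | 0.496 |
| Table 8, 84 per clinic | | 0.30 | 0.36 | 0.50 |

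Both choices of degrees of freedom round to Table 8. A one-sided 0.025 test on 9 df gives 0.269 at ICC 0.01 and does not match. The trial was therefore sized on a two-sided test.

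**Step 4: the literal rule at those effects.** Noncentral t on 9 df, with the critical value at +2.685 and noncentrality equal to effect/SE:

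| ICC | Effect (SD) | Noncentrality | Rule met, true β₂ positive | Rule met, true β₂ negative |
|---|---|---|---|---|
| 0.01 | 0.30 | 4.065 | 0.891 | 2.2 × 10⁻⁹ |
| 0.02 | 0.36 | 4.046 | 0.888 | 2.5 × 10⁻⁹ |
| 0.05 | 0.50 | 4.039 | 0.886 | 2.6 × 10⁻⁹ |

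For the correctly signed outcome, an ICP benefit makes β₂ positive, and the rule works with probability about 0.89. For the mis-signed outcome, an ICP benefit makes β₂ negative (last column), and an ICP harm of the same size makes it positive (about 0.89). The value is 0.89 rather than 0.90 because adding two t quantiles only approximates the noncentral t calculation. The two-sided test without a sign condition has the same power, about 0.89, for both outcomes.

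**The case against.** The strongest reply is that this is a slip of one word. The hypotheses already fix the direction for each outcome, Section 9.3 already requires two-sided p-values, and the Aim 2 rule is unsigned. On that reading 'positive' means favourable, no sensible analyst would report a rise in pain interference as success, and no estimate, p-value or sample size would change. The probabilities above only restate that the sign is reversed. The orientation of the scores is also inferred, and the EHR templates are in a separate appendix file that was not available for this check.

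Much of this stands. The wording probably is a slip, the numerical analysis is unaffected, and the probabilities describe only the literal rule. The orientation is an assumption, though it follows from the plan's own use of reducing interference and improving function.

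The reply does not rescue the rule. The text attaches the sign to the estimated coefficient, which is a numerical statement. A two-sided p-value does not remove an added sign condition. The unsigned Aim 2 rule shows that the sign is not a convention of the plan. A primary decision rule should not need readers to override it.

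**Conclusion.** The concern holds. The written success rule for the primary hypotheses has the wrong sign for exactly one of the two primary outcomes under either arm coding, and it conflicts with Sections 1.1 and 3. Only an unstated reversal of one scale, or a different arm coding for each outcome, would remove the conflict. Neither appears in the protocol text. Although the defect is confined to the stated direction, it should be corrected before analysis because it sits in the confirmatory criterion.

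**What to change.** In Section 9.6, Aim 1, replace the sign condition with two statements:

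1. The intervention indicator is 1 for ICP and 0 for CCP, and the scores are analysed so that higher pain interference is worse and higher physical function is better (to be confirmed against the scoring actually used).
2. Each β₂ is tested against 0, two-sided, at 0.025. ICP superiority is β₂ < 0 for pain interference and β₂ > 0 for physical function, and a significant result of the opposite sign is reported as favouring CCP.

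The sleep outcome is to be modelled in a similar way, so its orientation should be stated in the same place. The cost is a few lines of analysis-plan wording, with no change to data collection, model, alpha or sample size.

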9.2 Sample Size and Randomization

In **Table 8** below we present a range of minimum detectable effect size differences for the primary outcomes of Pain Interference or Function Scores for both the administrative sample (N=84 per clinic) and survey sample (N=42 per clinic) for 16 clinics (8 clinics randomized to each arm) for Aim 1. Sample size calculations for the cluster randomized design were based on the net difference between the two conditions across baseline and 3-months follow-up.⁵⁰ We assumed over time correlations of 0.50 for both patients (based on data from the [name] et al. pilot study³³ and summary data available for Durham VA clinics, intraclass correlation coefficients (ICC) of 0.01, 0.02, and 0.05 to account for clinic clustering, and also adjusted for the potential group-level randomization of up to 4 stratification variables as baseline covariate adjustments where we conservatively assumed no reduction in either group or subject level variance components. For all calculations, the type-I error is 2.5% to account for the multiple primary outcomes and power is conservatively assumed to be 90% to guard against deviations from assumptions. The number needed at baseline (N_b) is based on an attrition rate of 20%. Note in the **below Table 4** that the scenarios above lead to having adequate power to detect a medium effect size for the primary outcomes for both the administrative and survey samples.

Table 8. Minimum detectable effect size differences for 90% power, alpha of 0.025 and ICC of 0.01, 0.02, and 0.05 for administrative outcome (n=84 per clinic) and survey outcome (n=42 per clinic)

Number of clinics per condition	Number of patients per clinic needed at post-intervention follow-up (Total N)	Minimum Detectable Effect Size Difference ICC=0.01	Minimum Detectable Effect Size Difference ICC=0.02	Minimum Detectable Effect Size Difference ICC=0.05	Number of patients per clinic needed at baseline with 20% attrition (Total N_b)
8	42 (N=672)	0.37	0.42	0.55	53 (N_b =848)
8	84 (N=1344)	0.30	0.36	0.50	105 (N_b =1680)

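### Replacing the fixed 0.025 test of each primary outcome with Holm's step-down test would add power at the same 5% family-wise error; the plan should also say whether one or both outcomes must be significant

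*Combined protocol and SAP*

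**What the plan says.** Section 9.5.1 names two co-primary outcomes at 3 months: PROMIS pain interference and PROMIS physical function. Section 9.6 (Aim 1) tests the treatment-by-time coefficient for each by whether it is "significantly different than 0 at the 0.025 level due to 2 primary outcome variables". Section 9.3 sets the general rule as "two-sided p-values at the standard 0.05 level, except where noted due to multiple primary outcomes". No step-down or gatekeeping rule appears.

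The planning matches the analysis. In Section 9.2 "the type-I error is 2.5% to account for the multiple primary outcomes and power is conservatively assumed to be 90" per cent. The text there introduces Table 8 as giving detectable effects for one score or the other, so the 90% is power per outcome.

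Section 1.1 states the central hypothesis that "the ICP will reduce pain interference with normal activities and improve physical function"; the Précis and Section 3 repeat it in the same joined form. Section 9.6, by contrast, speaks of hypotheses in the plural and of estimating changes in one score *and/or* the other. The documents give no joint power, no correlation between the two outcomes, and no statement of whether success needs one outcome or both.

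**The concern.** The hypothesis names both outcomes, but the power statement covers each alone. With two tests each at 90% power, the chance that both are significant is below 90% unless they are perfectly correlated. The fixed split also holds the second outcome to 0.025 after the first has already been rejected. Control of the 5% family-wise error does not need that.

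Take p = 0.01 on one outcome and p = 0.04 on the other. The planned rule reports the second as not significant, whereas Holm rejects both at the same family-wise level. With 16 clinics, power is costly to buy by other means, so a free gain is worth taking.

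**Working it through.** **Inputs.** Section 9.2: "16 clinics (8 clinics randomized to each arm) for Aim 1"; 84 patients per clinic at follow-up in the administrative sample; "intraclass correlation coefficients (ICC) of 0.01, 0.02, and 0.05 to account for clinic clustering"; over-time correlation 0.50, used here for both patients and clinics; 0.025 per outcome, two-sided; 90% power. Table 7: 5 degrees of freedom spent on baseline covariates, leaving 16 − 2 − 5 = 9. *Assumption:* correlation r between the two test statistics from 0 to 0.9, because the documents give none.

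**Step 1: reproduce Table 8.** For m patients per clinic and g = 8 clinics per arm:

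variance = 4 × [(1 − ICC)(1 − 0.5) + m × ICC × (1 − 0.5)] / (m × g)

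detectable effect = √variance × (t₀.₉₈₇₅,₉ + t₀.₉₀,₉) = √variance × (2.685 + 1.383) = √variance × 4.068

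For m = 84 and ICC 0.01, variance = 4 × (0.495 + 0.42)/672 = 0.005446. Its root is 0.0738, and × 4.068 gives 0.300.

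| ICC | Recomputed | Table 8 |
|---|---|---|
| 0.01 | 0.300 | 0.30 |
| 0.02 | 0.362 | 0.36 |
| 0.05 | 0.504 | 0.50 |

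The plan's figures reproduce. The sum of t quantiles is an approximation: with noncentrality 4.068, the exact noncentral t gives 89.1% power per outcome. Exactly 90% needs a noncentrality of 4.127.

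**Step 2: both outcomes together.** Pairs of correlated t statistics were simulated (9 df, 500,000 pairs per setting), with both true effects at the detectable size (noncentrality 4.068). The fixed rule rejects each outcome if p ≤ 0.025. Holm rejects both if the smaller p ≤ 0.025 and the larger p ≤ 0.05.

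| r | Fixed: both | Fixed: at least one | Holm: both | Holm: each outcome |
|---|---|---|---|---|
| 0 | 79.3% | 98.8% | 89.9% | 94.4% |
| 0.3 | 80.4% | 97.8% | 90.1% | 94.0% |
| 0.5 | 81.4% | 96.8% | 90.3% | 93.5% |
| 0.7 | 83.0% | 95.3% | 90.9% | 93.1% |
| 0.9 | 85.6% | 92.8% | 91.3% | 92.1% |

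Under the fixed rule, power for each outcome is 89% throughout.

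**Step 3: sensitivity.** With power per outcome set at exactly 90%:

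- *Both significant, fixed rule:* 0.9 × 0.9 = 81.0% at r = 0, rising to 86.9% (normal) or 86.6% (t, 9 df) at r = 0.9.
- *Both significant, Holm:* 88.4% (normal) or 91.0% (t, 9 df) at r = 0; 91.1% or 92.1% at r = 0.9.
- *At least one significant:* 99.0% at r = 0, falling to about 93% at r = 0.9.
- *Each outcome under Holm:* about 92–95%; the top value arises only for the t with 9 df at r = 0.

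**Step 4: false positives.** With no effect on either outcome, the two rules have the same family-wise error, because each makes a first rejection only at 0.025. It is 5.0% at r = 0, 4.8% at 0.3, 4.4% at 0.7 and 3.7% at 0.9. With one true null, Holm's error is 4.4–4.7% and the fixed rule's is 2.5%. Holm therefore uses allowance that the fixed rule leaves idle, and stays within 5%.

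**Step 5: if both must succeed.** No split is then needed. Testing each at 0.05 gives joint power of 90–93% for r from 0 to 0.9 at the tabulated effects, equal to or slightly above Holm.

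**The case against.** The strongest objection is that nothing here is wrong. A fixed 0.025 split is valid, pre-specified, consistent between Sections 9.2 and 9.6, and gives simple simultaneous confidence intervals. That stands.

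A reader might infer that the trial has about 81% power, not 90%. The documents do not support this. They never claim 90% for the two outcomes together, and 81% would be the trial's power only under a rule that both must be significant, which is nowhere stated. The split itself, the plural hypotheses and the *and/or* in 9.6 fit a design in which either outcome may succeed alone; on that reading power is about 93–99%. The co-primary label and the joined hypothesis point the other way, so the rule is open. Nor can 81% be a single answer when no correlation is given.

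A reader might also infer that a trial with p = 0.01 and p = 0.04 fails its central hypothesis. Under the plan it would report one primary outcome significant and the other not; failure overall again presumes the unstated rule.

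It is also fair to say that Holm is not the natural test if both are required. With p = 0.03 and p = 0.04 it rejects neither, while testing each at 0.05 supports the joint claim. The fix therefore has to cover that case. What remains is that Holm never rejects less than the planned rule, whichever reading is meant.

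**Conclusion.** This is an efficiency gain available at almost no cost, together with a gap in the stated success rule. It is not an error. The 90% is right for what it describes.

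At the tabulated effects, the fixed rule gives about 79–87% for both outcomes and about 93–99% for at least one. Holm raises joint power to about 88–92% and power per outcome from about 89–90% to about 92–94%, with family-wise error still at most 5%. It does not change the chance that at least one outcome is significant.

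The figures assume that both true effects equal the detectable size, that the correlation between the tests lies between 0 and 0.9, and that the plan's variance model holds. The ranges span the plan's own noncentrality and exactly 90% power per outcome. That Holm never rejects less and controls the error does not depend on these assumptions.

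**What to change.** - **Section 9.6:** for the two Aim 1 tests, replace the fixed 0.025 rule with Holm. Test the smaller two-sided p-value at 0.025 and, if it is significant, the other at 0.05.
- **Section 9.2:** state that the tabulated 90% is power per outcome at the first step, and give joint power as a range over the assumed correlation. Tables 7 and 8 stay at 0.025.
- **Success rule:** say whether one significant outcome is enough. If both must succeed, say so and test each at 0.05 with no split, in place of Holm.
- **Timing:** make the change before any comparison of outcomes by arm. Section 6.3 says the statisticians are not blinded to clinic assignment, so the date of the change should be on record.

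The cost is a few sentences, with no change to sample size or data collection. The one drawback is that simultaneous confidence intervals matching Holm are less simple than those for the fixed split.

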1.2 Secondary Objectives

We will compare the effect of two different LBP pathways on sleep quality, as measured by PROMIS Short Form scores. We will also determine participant characteristics associated with greater improvements in pain and function, and better adherence to each care pathway. Planned and appropriately powered subgroup analyses for treatment moderators of previous opioid exposure and chronic vs. acute LBP will be completed. We will identify multidimensional subgroups from baseline characteristics for treatment moderation of pain and function, as well as for care strategy adherence. These additional analyses will inform the potential for identifying subgroup characteristics that indicated better clinical outcomes for Veterans in either care pathway.

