The survey outcomes for the enrolled subset of patients will be collected at baseline, 3, 6, 9, and 12 months and will include pain interference, function, intensity, catastrophizing, sleep, and depression (see Section 10 for full descriptions). These are all longitudinal continuous outcomes and a hierarchical linear model similar to that described for the primary aim will be fit. We will fit random coefficient models as described above (e.g. random intercept only, random intercept and linear slope) and assess using AIC model selection criteria to determine best model for the covariance structure. Similarly, we will determine the best model for the mean structure (e.g. linear, quadratic, dummy coding) as there are five outcome measurement occasions guided by descriptive plots and model fit assessed using AIC model selection criteria. Due to the timing of administration of baseline surveys that some baseline surveys may occur after the initial intervention contact, we will conduct sensitivity analysis treating baseline surveys after initial provider contact as occurring in the post-treatment period.

Aim 2 Analyses

As highlighted in the UG3 section we have strong clinical and scientific rationale to investigate chronic vs. acute LBP and previous opioid use vs. opioid naïve as *a priori* subgroups for treatment moderation.³⁸ We will define “chronic low back” as pain that has persisted for at least 3 months and resulted in pain on at least half the days in the past six months to be consistent with the NIH task force definition.⁴⁹ All participants will have chronicity of back pain assessed via the EHR template (see Section 6) at the time of initial referral to a given care pathway using questions specified in the NIH minimum dataset.⁴⁹ Opioid exposure prior to pathway entry will be defined as being prescribed at least one prescription opioid for 20 or more consecutive days (yes or no within 12 months prior to entering pathway).⁶⁴ This definition could be altered if different ones are suggested for use by the PMC3. These data will be obtained through VA’s Pharmacy Benefits Management System.

For the planned subgroup analyses for key moderators on the primary outcomes of pain interference and function will be the same modeling framework as described for AIM 1 with the addition of the indicator variable(s) for the moderator and associated interactions.⁶⁵ The fixed-effect portion of the model will have the form: $Y_{ijk} = \beta_0 +$

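### The primary model omits patient-level prior opioid exposure and chronicity, so if unblinded referral after clinic randomisation differs by arm, the treatment effect may carry avoidable case-mix bias

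*Combined protocol and SAP*

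**What the plan says.** Section 9.6 (Aim 1) fits a hierarchical linear model with "patients nested within clinics and baseline and 3 month values in the response vector". Treatment enters only through time: "The predictors in the model will include a time effect and indicator variables for treatment interacting with the time effect". The two arms therefore share one baseline mean. Adjustment covers the five clinic-level variables used in the constrained randomisation, among them "average level of opioid exposure of LBP patients at clinic, and average age of LBP patients at clinic", and "a limited number of patient-level covariates that are readily available in the EHR (age, gender, race and a comorbidity measure"). The printed model formula contains no covariates, so the plan does not say whether they enter as main effects only or also interact with follow-up.

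Section 9.6 (Aim 2) plans both missing variables for everyone. "All participants will have chronicity of back pain assessed via the EHR template" at initial referral. "Opioid exposure prior to pathway entry will be defined as being prescribed at least one prescription opioid for 20 or more consecutive days". This is a binary indicator covering the 12 months before entry, taken from VA pharmacy records. Section 1.2 gives them special standing: "Planned and appropriately powered subgroup analyses for treatment moderators of previous opioid exposure and chronic vs. acute LBP". They are used only in separate Aim 2 models, which have "the same modeling framework as described for AIM 1 with the addition of the indicator variable(s) for the moderator and associated interactions".

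On entry to the trial, Section 8 says that enrolment is governed by primary care referrals to the clinic's assigned pathway and assumes that about half of patients are referred. Section 9.2.1 says that patients, delivery staff and recruitment staff are unblinded. Section 9.3 limits the primary analysis to referred patients who had an initial contact.

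**The concern.** Randomising clinics balances clinics. It does not balance patients who are selected later by someone who knows the pathway. If providers at ICP clinics refer a different mix of chronic or opioid-exposed patients from those at CCP clinics, and those patients change differently over 3 months, the follow-up-by-intervention coefficient (β2) mixes treatment with case-mix.

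The clinic-average opioid covariate does not close this gap. Section 9.2.1 builds it from low back pain patients seen in the 3 to 6 months before clinic enrolment, so it says nothing about which of them are referred afterwards. No sensitivity analysis for case-mix is planned. At stake are the error rate and interpretation of the two co-primary comparisons, when the relevant data are already being collected.

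**Working it through.** **1. The plan's own figure.** Inputs from Section 9.2: 8 clinics per arm (g), 84 patients per clinic (m), over-time correlation r = 0.5, two-sided alpha 0.025, power 0.90. Table 7 gives 5 df for covariates, so df = 2(8 − 1) − 5 = 9.

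Detectable effect = (t[0.9875; 9] + t[0.90; 9]) × √{2 × 2(1 − r) × [1 + (m − 1)ICC] / (m g)}

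The t terms sum to 2.685 + 1.383 = 4.068.

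- ICC 0.01: 4.068 × √(2 × 1.83 / 672) = 0.300
- ICC 0.02: 4.068 × √(2 × 2.66 / 672) = 0.362
- ICC 0.05: 4.068 × √(2 × 5.15 / 672) = 0.504

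Table 8 states 0.30, 0.36 and 0.50, so it reproduces.

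**2. Bias in β2 from an omitted factor.** Let Δ be the arm difference in the share of patients with the factor, d0 its effect at baseline and d1 its effect at 3 months, in SD units. With a common baseline mean and r = 0.5 at both patient and clinic level, generalised least squares gives:

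- factor omitted: bias = Δ × (d1 − 0.5 d0)
- main effect only: bias ≈ 0.75 × Δ × (d1 − d0)
- main effect plus follow-up interaction: bias = 0

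**3. Numbers.** The documents give none of Δ, d0 or d1, so all three are assumptions. The calculation uses 80 patients per clinic so that shares of 60%, 70% and 80% are whole numbers. Each cell shows the bias at Δ = 10 / 20 points, in SD.

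| d0, d1 | Omitted (as planned) | Main effect only | With follow-up interaction |
|---|---|---|---|
| 0.3, 0.3 | 0.015 / 0.030 | 0 / 0 | 0 / 0 |
| 0, 0.3 | 0.030 / 0.060 | 0.023 / 0.045 | 0 / 0 |
| 0.2, 0.5 | 0.040 / 0.080 | 0.023 / 0.045 | 0 / 0 |
| 0.3, 0.6 | 0.045 / 0.090 | 0.023 / 0.045 | 0 / 0 |
| 0, 0.5 | 0.050 / 0.100 | 0.038 / 0.076 | 0 / 0 |

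Example: Δ = 0.10, d0 = 0.3, d1 = 0.3 gives 0.10 × (0.3 − 0.15) = 0.015. Half of the raw 0.030 difference is already removed by the baseline score. The most adverse pairing of the same limits, d0 = 0 with d1 = 0.6, is not in the table; by the formula it gives 0.20 × 0.6 = 0.12 at 20 points.

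**4. Scale.** Relative to the detectable effects, 0.015/0.50 = 3% and 0.10/0.30 = 33%. The SE of β2 is about 0.065 at ICC 0.01 and 0.108 at ICC 0.05. With 9 df and a nominal 2.5% two-sided test, the noncentral t gives these true error rates under no treatment effect:

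| Bias (SD) | ICC 0.01 | ICC 0.05 |
|---|---|---|
| 0.015 | 2.8% | 2.6% |
| 0.045 | 5.3% | 3.5% |
| 0.09 | 15% | 6.6% |

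**5. Price of adjusting.** Across the three models the SE runs from 0.0648 to 0.0657 at ICC 0.01 and from 0.1077 to 0.1082 at ICC 0.05. This was computed for one patient-level factor. Patient-level terms spend no clinic-level df.

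**The case against.** A reader might infer that case-mix differences are certain to sit in the treatment effect. The documents do not support that. No imbalance is shown, and several features lower the chance of one. Referral criteria are common and trained (Section 4.1), each clinic offers one pathway, treating providers are not told about the other pathway (Section 6.3), and allocation is constrained on clinic pain, opioid exposure and age (Section 9.2.1). These stand as mitigation. They do not remove a provider's discretion over whom to refer to the one pathway on offer.

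It is also tempting to read moderators as prognostic factors. The protocol names the two variables as moderators and nowhere says that such patients improve less. That they predict change is an assumption here.

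The baseline score already takes out the case-mix that it reflects; the formula above allows for this. At 10 points, every bias in the table is below one SE. Aim 2 already fits each factor with its follow-up interaction, so effects by stratum will exist. What is missing is one overall adjusted estimate.

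Chronicity has a real weakness: in both arms it is recorded by unblinded pathway staff after allocation (Section 6.1, Tables 4 and 5), so its measurement could itself differ by arm. The pharmacy-based opioid variable is safer.

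Finally, a reader might think that the missing-at-random assumption rests on age, sex, race and comorbidity. The Missing Data text ties it to previous outcomes and design variables, and says only that those four may strengthen it. Its auxiliary variables serve missing-data sensitivity, not case-mix.

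**Conclusion.** The concern holds as a risk that the plan leaves open at almost no saving. Two baseline variables planned for the whole sample, and given prominence by the protocol, are missing at patient level from the primary model, while selection into the analysis is unblinded and follows randomisation.

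If referral differs by 10 to 20 points between arms and the factor predicts outcome as assumed, the bias is about 0.015 to 0.10 SD in the five settings, or 3% to 33% of the detectable effect. It is largest for a factor that predicts recovery rather than baseline severity. The range rests on assumed imbalance and effects, r = 0.5, and the common-baseline model as written. The form of adjustment matters: β2 is a difference in change, so a main effect alone can leave up to 0.076 SD in these settings. That limit would also apply to the listed patient covariates if they enter as main effects only.

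**What to change.** Amend Section 9.6 (Aim 1) before any comparative outcome data are examined:

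1. Add patient-level prior opioid exposure (yes/no, pharmacy data, 12 months before entry) with its follow-up interaction to the primary model. Lock its definition, since Section 9.6 allows it to change.
2. State that age, gender, race and comorbidity enter with their follow-up interactions.
3. Add chronicity with its follow-up interaction, either in the primary model or, because of how it is recorded, in a named sensitivity analysis.
4. Report both factors by arm among referred patients.

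Follow-up interactions for the five clinic-level covariates should not be required; with 16 clinics their cost is debatable.

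The cost is plan wording, a few more patient-level terms and a rule for missing chronicity values. No new data are needed. The change adjusts only for what is measured; imbalance in unmeasured case-mix would remain.
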